Effect of pre-operative tizanidine on postoperative urinary retention after sacrospinous vaginal vault suspension: a pilot study

Principal Investigator
[name] [name]

Co-PI
[name]

Clinical Research Supervisor
[name]

Sub-Investigator(s)
[name] MPH
[name]
[name]
[name]
[name]

Sponsor
None

Site of Investigation
Northshore University Health System

Date of Protocol: 6/4/2025

Protocol Version: 1

Purpose

The purpose of this study is to evaluate the effect of tizanidine on postoperative urinary retention after sacrospinous vaginal vault suspension compared with baseline data.

Background

Postoperative urinary retention has been defined as the inability to void despite having fluid in the bladder during the postoperative period (1). Urinary retention after pelvic reconstructive surgery requiring indwelling catheter or self-catheterization usage occurs in approximately 30-60% of patients postoperatively (1,2,3). Our prior retrospective chart review reviewing postoperative urinary retention rates after pelvic reconstructive surgery demonstrated postoperative urinary retention after a sacrospinous vaginal vault suspension to be approximately 78.9%.

Each patient after surgery undergoes a “voiding trial” where their voided volume is compared to their post-void residual volume. “Passing” a voiding trial has traditionally been defined as voiding a greater volume than the post-void residual volume (4). If the patient does not “pass” the voiding trial, the patient is characterized as having postoperative urinary retention and is discharged home with an indwelling catheter to prevent detrusor injury from bladder overdistention, pain and urinary tract infection (5).

Many women consider being discharged home with a Foley catheter to be a surgical complication and describe catheter use as the worst aspect of their surgery (1,6). Indwelling catheters are the leading cause of hospital-acquired urinary tract infections (UTIs), are often a source of embarrassment and inconvenience for patients, and often require additional office visits and healthcare utilization (7).

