The leading hypotheses regarding the incidence of postoperative urinary retention after sacrospinous ligament suspension includes postoperative pain and pelvic floor muscle spasm leading to retention. The sacrospinous suspension includes a suture that is passed through the sacrospinous ligament and, therefore, through the coccygeus muscle with irritation of the pudendal nerve (8). The pelvic floor is a synergistic team of muscles that work together to support the pelvic organs and spasm of the coccygeus muscle, rather than an isolated muscle, can cause spasm of the entirety of the pelvic floor leading to retention. Tizanidine is a muscle relaxant which can work to alleviate this spasm and, theoretically, prevent postoperative urinary retention (9). Tizanidine also works as an alpha-adrenergic receptor blocker which can increase smooth muscle relaxation around the urethra specifically and, theoretically, improve urine flow (9).

Tizanidine is also frequently given for postoperative pain after sacrospinous ligament suspension and may act as an adjunct to a non-narcotic pain regimen to improve postoperative pain while reducing narcotic use after surgery. Postoperative buttock and posterior thigh pain are common symptoms after SSLF, with immediate pain reported in 6–84% of patients and persistent pain at 6 weeks occurring in 1–15% (7). Untreated acute postoperative pain has been shown to lead to increased morbidity and mortality (10). Pain is the most common reason for a postoperative unplanned hospital admission and poor postoperative pain control can lead to decreased ambulation, increased incidence of thromboembolism, and decreased inspiratory effort leading to postoperative pneumonia, therefore postoperative pain control is critical (11,12). In a country with rising narcotic-use and dependence, it is critical that we continue to explore non-narcotic alternatives for patients after surgery.

Postoperative urinary retention is extremely common after pelvic reconstructive surgery involving a sacrospinous vaginal vault suspension and is extremely bothersome to patients. Tizanidine is a low-risk,

well tolerated, cost-effective medication (9). No study to date has evaluated preoperative administration of tizanidine for postoperative urinary retention.

Hypothesis

We hypothesize that providing tizanidine preoperatively will improve postoperative urinary retention rates compared with our previously defined baseline data.

Objectives

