Patients who are undergoing a sacrospinous ligament suspension will be enrolled (after the previously described informed consent discussion) to receive a single preoperative dose of tizanidine 2mg or in the preoperative holding area on the day of their scheduled surgery as well as continued tizanidine postoperatively as needed every 6 hours.

After surgery, patients will then undergo a voiding trial in the recovery area. As described in prior studies, the patient will fail the voiding trial if voided volume is less than the PVR volume. Upon failing the voiding trial, the patient will be discharged home with a Foley catheter with plan for outpatient Foley catheter removal, consistent with our current protocol. According to our current protocol, patients discharged with a Foley catheter can either remove the catheter at home in 48-72 hours after surgery or call our office to have it removed at the next available appointment within 2-5 days postoperatively.

We will then evaluate the rate of postoperative urinary retention after administration of tizanidine compared with our previously studied and documented postoperative urinary retention incidence after sacrospinous ligament. Any collected information will be de-identified.

The current rate of postoperative urinary retention at our institution based on chart review after sacrospinous ligament suspension is 78.9%. Based on a sample size calculation to achieve 80% power, to evaluate for a 50% decrease in our urinary retention rate (from 78.9% to approximately 39.5%) we will need 23 subjects total. We aim to complete 23 subjects and expect to enroll 30 subjects to account for participant dropout.

Postoperative pain data will be evaluated by reviewing postoperative pain scales documented by the nursing staff in the postoperative area on a Likert scale 0-10. We will also evaluate narcotic administration in the postoperative area as a proxy for pain.

Inclusion criteria

Sacrospinous ligament suspension (CPT 57282)

Exclusion criteria

Age <18

Planned combined cases with colorectal surgery, general surgery, or gynecology-oncology

Known history of urinary retention

Known contraindication to tizanidine

Concomitant use of the following:

- Fluvoxamine, Ciprofloxacin (Patients are eligible if 3-5 half-lives have passed since they have taken Fluvoxamine, Ciprofloxacin)
- Potent CYP1A2 inhibitors
- Oral contraceptive
- Alpha-adrenergic agonists

Stage 4 Chronic Kidney Disease (eGFR <30), or worse

Breastfeeding

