Hypersensitivity to tizanidine

Pre-existing psychiatric illness

Hypotension and chronic hypotension (<90/50 mmHg)

Variables

MRN

Age (at time of surgery)

Gravity and para

Race/ethnicity

Smoking status

Menopausal status

BMI

Comorbid conditions

Diabetes

Hypertension

Other cardiovascular disease

Respiratory disease

Obstructive sleep apnea

Chronic pain conditions

Prior hysterectomy

Prior abdominal surgery

History of prior prolapse surgery

History of prior incontinence surgery

Continence status

Prolapse stage

Location of surgery (Highland Park Hospital, Evanston)

Type of anesthesia

ASA grade

Incontinence procedure

Mid-urethral sling placement: CPT 57228

Concomitant prolapse procedures

Anterior colporrhaphy: CPT 57240

Posterior colporrhaphy: CPT 57250
Combined anterior and posterior colporrhaphy: CPT 57265
Hysterectomy
Rectopexy
Intraoperative complications
Additional procedures (ie. lysis of adhesions)
Intraoperative consultations
Length of procedure
Estimated blood loss
Surgeon
Surgeon experience (< 5 years, > 5 years)
Total time in PACU
Time of day in ASU
Total time in ASU
Immediate postoperative complications
Uncontrolled pain
Postoperative pain scores upon admission to the ASU
Postoperative pain scores at discharge
Reason for postoperative admission (surgeon choice, comorbid conditions, nausea/vomiting, etc.)
Time from voiding trial to void
Postoperative urinary retention
Postoperative urinary tract infection (UTI)
Unanticipated healthcare encounters
Urogynecology office visit (excluding voiding trial(s))
ED visit
Readmission within 30 days of discharge
Unplanned phone calls
Complications 30 days after discharge
Urinary tract infection
Reoperation
Venous thrombotic event

Statistical Methodology

A statistician from the NorthShore Research Institute will assist with statistical analysis. Data will be analyzed using SAS 9.4 (SAS Inc., Cary, NC). Demographic and clinical characteristics between groups will be compared using Student t-test (parametric) or Mann-Whitney U test (nonparametric) for continuous variables and Chi-squared test or Fisher exact test for categorical variables. Multivariable logistic regression models will be constructed to examine the relationship of an outcome with demographic and clinical covariates. Statistical significance will be defined at p-value < 0.05.

Literature review

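### The plan does not say whether the 78.9% benchmark excluded patients with prior urinary retention, as the trial does; restrict it to match, or state that it matches, before crediting a moderate fall to the drug

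*Combined protocol and SAP*

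**What the plan says.** The Background introduces the benchmark as the result of the site's own retrospective chart review, which "demonstrated postoperative urinary retention after a sacrospinous vaginal vault suspension to be approximately 78.9" percent. Methods repeats it: "The current rate of postoperative urinary retention at our institution based on chart review after sacrospinous ligament suspension is 78.9" percent. The Hypothesis is that the drug "will improve postoperative urinary retention rates compared with our previously defined baseline data", and Methods says that the observed rate will be "compared with our previously studied and documented postoperative urinary retention incidence after sacrospinous ligament". There is no concurrent control arm.

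The Exclusion criteria include "Known history of urinary retention" and "Planned combined cases with colorectal surgery, general surgery, or gynecology-oncology", along with renal, psychiatric, blood-pressure and drug-interaction exclusions.

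The benchmark is described only by procedure and institution. Its eligibility criteria, numerator, denominator and dates are not given.

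Statistical Methodology says "Demographic and clinical characteristics between groups will be compared", and that "Multivariable logistic regression models will be constructed to examine the relationship of an outcome with demographic and clinical covariates". It names no covariates and does not commit to an adjusted primary comparison. The Variables list has no item for retention history before surgery.

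**The concern.** With no concurrent control, the benchmark carries the primary conclusion. One of the trial's exclusions concerns the same condition as the primary outcome. If the chart review included patients with prior retention, and they failed the voiding trial more often than the rest, then trial-eligible patients would have a rate below 78.9% without any drug. Part of an observed fall would then be selection.

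Of the trial's exclusions, this is the one with a natural expected direction. The others could move the rate either way or not at all. The planned regression does not clearly deal with it. Because prior retention is an exclusion, the treated group contains no such patients, so the direct remedy is to restrict the historical cohort.

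**Working it through.** **Inputs from the documents.** Benchmark 78.9%; target about 39.5%; 23 completers; 80% power; significance at p < 0.05 (sidedness not stated, two-sided assumed).

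**Inputs assumed, because the documents give none.** f = share of the review cohort with prior retention (5%, 10%, 20%). r = their failure rate (90%, 100%). Historical n = 38, 76 or 133, for which 30/38, 60/76 and 105/133 all equal 78.9%.

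**The plan's own figures.** Half of 78.9% is 39.45%, as stated. A two-sample comparison of 78.9% with 39.5% (two-sided 0.05, 80% power) needs 24 per group by the normal approximation and 22.9 by the arcsine formula. So 23 reproduces as a per-group size. Nothing below depends on how it was derived.

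**Step 1: no-drug rate in eligible patients.** e = (0.789 − f·r)/(1 − f). For f = 10%, r = 100%: (0.789 − 0.100)/0.900 = 0.766.

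| f | e, r = 90% | e, r = 100% |
|---|---|---|
| 5% | 78.3% | 77.8% |
| 10% | 77.7% | 76.6% |
| 20% | 76.1% | 73.6% |

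If r = 78.9%, or if the review already excluded these patients, the shift is zero.

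**Step 2: could selection alone produce the planned effect?** Setting e = 0.395 with r = 100% gives f = (0.789 − 0.395)/(1 − 0.395) = 0.394/0.605 = 0.651. About 65% of the review cohort would have to be ineligible and all in retention.

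**Step 3: chance of a false benefit, Fisher.** Enumerate Bin(n, 0.789) × Bin(23, e) and sum the probability where two-sided Fisher p < 0.05 and the trial rate is lower. Results are for n = 38/76/133.

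| f | r = 90% | r = 100% |
|---|---|---|
| 0 (no mismatch) | 1.9/2.0/2.3% | 1.9/2.0/2.3% |
| 5% | 2.1/2.4/2.7% | 2.4/2.7/3.0% |
| 10% | 2.5/2.8/3.1% | 3.1/3.6/4.1% |
| 20% | 3.4/3.9/4.5% | 5.5/6.5/7.6% |

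With the restricted cohort as comparator, the chance is 1.6-2.2% in every mismatch case.

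**Step 4: chance of a false benefit, fixed benchmark.** If 78.9% is treated as a known constant, the two-sided exact binomial test (minimum-likelihood) rejects at 14/23 or fewer (p = 0.042). P(X ≤ 14) for X ~ Bin(23, e) is 3.8% with no mismatch. With r = 100% it is 5.1%, 6.8% and 12.6% at f = 5%, 10% and 20%. A stricter rule with a lower tail of at most 0.025 rejects at 13/23 or fewer; the chance goes from 1.3% to 1.9%, 2.7% and 5.7%.

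**Step 5: which results could change?** Largest significant trial count out of 23 by Fisher, with prior-retention patients removed at r = 100%:

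| Historical n | Unrestricted | f = 10% removed | f = 20% removed |
|---|---|---|---|
| 38 | 12 v 30/38, p = 0.045 | 11 v 26/34, p = 0.046 | 10 v 22/30, p = 0.047 |
| 76 | 12 v 60/76, p = 0.017 | 12 v 52/68, p = 0.036 | 11 v 45/61, p = 0.037 |
| 133 | 13 v 105/133, p = 0.033 | 12 v 92/120, p = 0.022 | 12 v 78/106, p = 0.049 |

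For example, 12/23 gives p = 0.045 against 30/38 but 0.086 against 26/34. Against a fixed benchmark, 14/23 gives 0.042 at 78.9% but 0.086 at 76.6%, and 13/23 gives 0.017 at 78.9% but 0.093 at 73.6%. The sensitive counts of 11 to 14 are observed rates of 47.8% (11/23) to 60.9% (14/23), which are relative falls of 39% to 23%.

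At the planned effect (9/23 = 39.1%), Fisher p is 0.0025/0.0006/0.0002 unrestricted. In the worst case above (f = 20%, r = 100%) it is 0.023/0.005/0.003, still significant.

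**The case against.** **No mismatch is shown.** The documents summarise the review in a sentence or two, and silence in a short pilot protocol is not evidence of bias. This stands. A reader might infer that the 78.9% is inflated; the documents do not support that, because they do not say who was in the review.

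**Direction and size are assumed.** Nothing in the documents says that patients with prior retention fail more often, and f, r and the historical n are all missing. This also stands, and it is why the point is conditional. With a benchmark already at 78.9%, such patients have little room to do worse.

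**The planned analysis handles it.** In part. The Variables list covers continence status, prolapse stage, prior surgery and concomitant procedures, and the benchmark comes from the same institution and procedure. Retention history in the historical cohort is not covered.

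**The voiding-trial definition might also differ.** A reader might infer this, but nothing supports it: Background and Methods give the same rule, voided volume against residual volume.

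**A sensitivity analysis would suffice.** Restriction does cost power and may make the benchmark less favourable. Still, like-for-like eligibility is the less biased comparator, and naming it before analysis prevents a choice between benchmarks once results are known.

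**It is a pilot.** True, but the protocol states a hypothesis, a power calculation and a significance threshold, so a benefit may be claimed.

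**Conclusion.** The omission is real and minor. The primary conclusion rests on a rate whose eligibility is not stated, while the trial excludes patients with a history of the outcome condition. Under the assumed inputs, the eligible no-drug rate is about 1 to 2 points lower at a 5-10% share if nearly all of those patients failed, and up to about 5 points lower at 20%. Only a moderate fall is sensitive: about 11-13 of 23 by Fisher, or 13-14 of 23 against a fixed 78.9%.

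A reader might infer that the error rate would exceed 5%. Under Fisher that happens, among the cases examined, only at a 20% share all in retention. Against a fixed 78.9% with the 14/23 cut-off it happens, marginally, from a 5% share all in retention (5.1%). The answer therefore depends on a test that the plan does not name. A reader might also infer that the planned halving could be selection; that would need about 65% of the review cohort to be ineligible and all in retention. If the review already excluded these patients, this bias is zero.

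**What to change.** Before analysis, apply the trial's exclusions to the existing chart-review cohort: at least prior urinary retention and planned combined cases, and the others as far as the charts allow. Use the restricted cohort, with its numerator and denominator, as the primary comparator. Keep the unrestricted 78.9% as a sensitivity analysis and state which criteria could not be applied. Retention history is needed for the historical cohort only. If the review already applied these criteria, a sentence saying so with the counts closes the point.

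The cost is a sentence or two of SAP wording and a query of the review data, or a new chart look-up if retention history was not recorded; the documents do not say which. The historical denominator shrinks and the benchmark may become less favourable. For a treated rate of 39.5%, Fisher power at assumed historical n = 38/76/133 goes from 85/93/95% to about 77/88/91% (10% share, all in retention) or 67/80/86% (20% share, all in retention). Part of that loss is the smaller true gap (76.6 − 39.5 = 37.1 points at a 10% share, against 78.9 − 39.5 = 39.4), not the restriction itself.

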The **primary objective** of this study is to evaluate whether preoperative administration of tizanidine will decrease the rate of postoperative urinary retention sacrospinous vaginal vault suspension compared with previously defined data. The **secondary objective** of this study is to evaluate for any differences in postoperative pain after administration of tizanidine compared to previously defined data.

Specific Aims

1. Evaluate the postoperative urinary retention rate in patients undergoing sacrospinous ligament suspension after postoperative administration of tizanidine.
2. Evaluate the postoperative pain scores after postoperative administration of tizanidine in patients undergoing sacrospinous vaginal vault suspension (postoperative nursing documentation performed in the recovery area based on a Likert scale of 0-10) and compare the differences in postoperative pain with previously collected data.
3. Evaluate the difference in unplanned admission the day of surgery or unplanned admission within 30 days after surgery, unplanned office visits within 30 days after surgery or Northshore encounters within 30 days after surgery after postoperative administration of tizanidine. These medical encounters will include any need for additional medical treatment, phone calls, complications or patient concerns within 30 days postoperatively. This data will be collected via chart review.

Outcome measures

1. Primary outcome measure:
 - a. Determine the postoperative urinary retention rates in patients undergoing a sacrospinous ligament suspension after postoperative administration of tizanidine. This will be determined immediately postoperative in the postoperative recovery room based on whether patients pass or fail their voiding trial described above. The result will be documented in electronic medical records and obtained from chart review.
2. Secondary outcome measures:
 - a. Determine differences in postoperative pain after postoperative administration of tizanidine. This data will be obtained by electronic data pull and chart review.
 - b. Determine the difference in unplanned admissions, office visits or Northshore encounters within 30 days after surgery after postoperative administration of tizanidine. This data will be collected via chart review.

Methods

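### Does the missing rule for an operated patient without a recovery-room voiding trial put the primary result at risk?

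*Combined protocol and SAP*

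**What the plan says.** The sample-size paragraph in Methods plans on 23 completers out of 30: "We aim to complete 23 subjects and expect to enroll 30 subjects to account for participant dropout". No dropout rate, reason or definition is attached.

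Outcome measure 1a sets the time and place of the primary outcome: "This will be determined immediately postoperative in the postoperative recovery room based on whether patients pass or fail their voiding trial". The Methods section expects this for everyone: "After surgery, patients will then undergo a voiding trial in the recovery area". Background likewise describes a trial for each patient after surgery and classes a patient who does not pass as having retention. Failure compares two measured volumes, so it presupposes that a trial took place. The stated sequel is "Upon failing the voiding trial, the patient will be discharged home with a Foley catheter".

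Specific Aim 3 also counts "unplanned admission the day of surgery", and the Variables list includes "Reason for postoperative admission (surgeon choice, comorbid conditions, nausea/vomiting, etc".

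Statistical Methodology offers "Chi-squared test or Fisher exact test for categorical variables", logistic regression, and "Statistical significance will be defined at p-value < 0.05". It gives no analysis set and no missing-outcome rule.

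**The concern.** Some women will be admitted on the day of surgery, whether by surgeon's choice or for nausea. If such a woman never has her recovery-room trial, the definition gives her no outcome. She could be counted as retention, counted as no retention, or left out.

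If untested women are left out and are in retention more often than average, the observed rate is too low and the drug looks better than it is. The comparator is a historical rate, and the protocol does not say how the chart review behind 78.9% treated untested patients. One patient in 23 is 1/23 = 4.3 percentage points, so a rule chosen after seeing the data could decide a close result.

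**Working it through.** **Inputs.** Baseline rate 78.9%, target about 39.5%, 80% power, 23 completers and 30 enrolled (Methods); threshold 0.05 (Statistical Methodology). Assumptions: the test, its sidedness, the baseline cohort size and the number of untested patients, none of which the documents give.

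**The plan's own figure.** The arcsine formula for two proportions, two-sided 0.05, has h = 2·arcsin√0.789 − 2·arcsin√0.395 = 2.187 − 1.359 = 0.828. Then n = 2·(1.960 + 0.842)²/0.828² = 22.9, so 23. That is a per-group size for comparing two samples. A one-sample test against a fixed 78.9% needs about 10 (normal approximation, 9.4), so 23 leaves slack for that comparison. The allowance is 30 − 23 = 7, or 7/30 = 23.3%.

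**Planned effect.** 39.5% of 23 is about 9 retained. If all seven spare enrolments were dosed, operated on and untested, the bounds are 9/30 = 30% and 16/30 = 53%. The exact binomial lower tail against 0.789 is 0.00004 for 9/23 and 0.0016 for 16/30 (two-sided 0.0024).

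**Borderline results.** Exact binomial against 0.789, with each untested patient added as retained:

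| Retained/n | Added | One-sided p | Two-sided p |
|---|---|---|---|
| 13/23 | 0 | 0.013 | 0.017 |
| 16/26 | 3 | 0.033 | 0.0496 |
| 17/27 | 4 | 0.043 | 0.056 |
| 18/28 | 5 | 0.054 | 0.065 |
| 20/30 | 7 | 0.083 | 0.116 |
| 14/23 | 0 | 0.038 | 0.042 |
| 15/24 | 1 | 0.049 | 0.074 |

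From 13/23, significance goes at three added patients under one-sided 0.025, four under two-sided 0.05, and five under one-sided 0.05. From 14/23, one added patient is enough under two-sided 0.05. If the true rate is 39.5%, the chance of 13 or more retained of 23 is about 7%.

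**False positives with no drug effect.** Let 30 be operated on at an overall rate of 0.789 (expected 23.67 retained), and leave out m patients whose retention is q. The assessed rate is r = (23.67 − m·q)/(30 − m). Reject when the count is at most c, the largest value with lower tail at or below 0.025 under 0.789.

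| m left out | c of n | q = 0.789 | q = 1 |
|---|---|---|---|
| 1 | 17/29 | 1.1% | 1.4% |
| 2 | 17/28 | 2.2% | 3.5% |
| 3 | 16/27 | 1.6% | 3.4% |
| 7 | 13/23 | 1.3% | 7.4% |

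The q = 0.789 column moves only because c is a whole number. With q = 0.9 the rate is 2.5% at m = 3 and 3.6% at m = 7. Exceeding 7% takes seven untested patients, all in retention.

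**Fisher's exact test, two-sided, assumed baselines at 78.9%.** The planned result in the seven-patient worst case (16/30) gives p=0.003 against 300/380, 0.037 against 30/38 and 0.127 against 15/19. At the margin, 12/23 against 30/38 gives p=0.045, and one added retained patient (13/24) gives 0.051.

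**What the text implies about frequency.** The dose is given in preoperative holding and the trial takes place in the recovery area after surgery, so there is little time between dosing and outcome in which to lose a patient. Consent may come at a visit before surgery, so withdrawals and cancelled operations can fall before dosing. Those losses cannot bias the rate among operated patients. Admission may also follow a completed trial.

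**The case for a change.** The strongest argument for a change is that the gap is real and would be cheap to close. Background's statement that a patient who does not pass has retention concerns someone who was tested. The study, though a pilot, states a hypothesis, a power and a threshold. All participants are to receive the drug, and outcomes are read from charts, so a rule settled late could be settled to suit. The crossing of 0.05 appears with both the one-sample and the Fisher comparison, sometimes with a single patient. With a baseline as small as 19, even the planned result fails in the worst case.

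What stands is that the rule is unstated and that a close result could depend on it. What does not stand is the step from foreseen admissions to missing primary outcomes, since the documents place every patient's trial in the recovery area. The seven-patient scenario uses the whole allowance on the one kind of loss that matters, which is an extreme. The 15/19 result depends on that scenario and on an assumed cohort size. The remedy would ask for a counting rule without showing which rule is right, because the baseline's handling is unknown.

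**Conclusion.** No change to the plan follows. This is missing detail that an analyst would fill sensibly: analyse the patients who were dosed, operated on and tested, report how many were not tested and why, and show the result with all of them counted each way. The Variables list already collects retention status and reason for admission. No stated rule gives a wrong answer, and followed as written the plan yields an outcome for every operated patient.

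The planned effect is safe against a fixed 78.9% even in the extreme case (16/30, one-sided p=0.0016). With one to three patients left out, the false-positive rate stays at or below about 3.5% against a nominal 2.5%, even if all are in retention. Only a borderline result is exposed, and only if untested patients occur. The conclusion rests on the protocol's statement that all patients undergo the trial in recovery, on few exceptions to it, and on an assumed exact test. It would be weaker if the baseline cohort were very small or if trials were often not done.

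### Narcotic use in recovery cannot stand in for pain when participants may also receive as-needed tizanidine and analgesic doses are not listed for collection

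*Combined protocol and SAP*

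**What the plan says.** The stated secondary objective is whether postoperative pain differs from past data. Specific Aim 2 takes nurse-recorded scores from the recovery area and will "compare the differences in postoperative pain with previously collected data". The pain paragraph in Methods repeats that measure ("reviewing postoperative pain scales documented by the nursing staff in the postoperative area on a Likert scale 0-10") and then adds a second one: "We will also evaluate narcotic administration in the postoperative area as a proxy for pain".

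The intervention paragraph in Methods gives each participant a single dose before surgery "as well as continued tizanidine postoperatively as needed every 6 hours".

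One sentence in the Background covers both usual care and the expected effect. It opens "Tizanidine is also frequently given for postoperative pain after sacrospinous ligament suspension" and goes on to say that the drug "may act as an adjunct to a non-narcotic pain regimen to improve postoperative pain while reducing narcotic use after surgery".

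The Variables list has pain entries (for example "Postoperative pain scores upon admission to the ASU", a score at discharge, and uncontrolled pain) but no narcotic dose and no tizanidine dose. Statistical Methodology gives general group tests and logistic regression. It has no rule for reading narcotic use together with pain scores or with tizanidine taken.

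**The concern.** A proxy for pain is useful only if it relates to pain in the same way in the two cohorts being compared. Here the study drug is itself used against pain, and the protocol's own rationale includes a possible reduction in narcotics. Narcotic use can then fall for at least two reasons: patients hurt less, or patients with the same pain receive tizanidine where they would otherwise have received a narcotic.

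The design offers little protection. The comparator is historical, no blinding is described, and participation is recorded in the patient's chart, so recovery staff can know who is in the study. At stake is the reading of the secondary objective: a fall in narcotic use could be reported as support for a pain benefit when the data cannot show that pain changed.

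**Working it through.** The plan gives no narcotic rate, no target for this measure and no power for it, so there is no figure to reproduce. The check sets the sections side by side and then illustrates the mechanism with assumed inputs.

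**Step 1: does the text support the mechanism?**
- Methods, pain paragraph: narcotic use is given the role of a stand-in for pain.
- Methods, intervention paragraph: tizanidine may be taken after surgery when needed, at six-hourly intervals, following the preoperative dose.
- Background: tizanidine is used for postoperative pain and may lower narcotic use.

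Together these make narcotic use a quantity that the study regimen can change by a route other than pain. That is enough to defeat the proxy reading in principle.

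**Step 2: could the planned data detect it?** Separating the routes would need at least the narcotic and tizanidine doses in the same window, in both cohorts. The Variables list has neither. The intention to evaluate narcotics appears only in Methods.

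**Step 3: how large could it be?** All inputs here are assumptions. Let *q* be the share of patients needing an analgesic in recovery, the same in both cohorts (pain unchanged). Let *s* be the share of that need met by tizanidine with no narcotic given. Then

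narcotic rate = *q* × (1 − *s*).

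| Need *q* | *s* = 0 | *s* = 10% | *s* = 25% | *s* = 50% |
|---|---|---|---|---|
| 40% | 40% | 36% | 30% | 20% |
| 60% | 60% | 54% | 45% | 30% |
| 80% | 80% | 72% | 60% | 40% |

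If the historical cohort had *s* = 0, the rate falls by 10% to 50% in relative terms over these non-zero shares, and not at all if *s* = 0 in the trial too.

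**Step 4: allow for tizanidine in the historical cohort.** With shares *s*₀ (historical) and *s*₁ (trial), the ratio of narcotic rates at unchanged pain is (1 − *s*₁)/(1 − *s*₀), whatever the value of *q*.
- *s*₀ = 25%, *s*₁ = 50%: 0.50/0.75 = 0.67, a fall of one third.
- *s*₀ = *s*₁ = 25%: 0.75/0.75 = 1.00, no distortion.
- *s*₀ = 25%, *s*₁ = 10%: 0.90/0.75 = 1.20, a rise of one fifth.

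The distortion depends on the difference in exposure between cohorts. The documents report exposure for neither.

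**The case against.** The strongest reply is that pain is already measured directly. Specific Aim 2 is about the 0-10 score, Methods names that score first, and narcotic use appears in no objective, aim or outcome measure. To claim better pain control on narcotic use alone, the investigators would have to set aside their own main measure. This stands, and it limits the weight of the point. It does not justify the word proxy, because the plan does not say what follows if the two measures disagree.

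A second reply is that substitution is not shown to operate in the measured window. Narcotics are assessed only in the recovery area, the as-needed doses follow a preoperative dose at six-hourly intervals, and nothing says that staff give tizanidine before or instead of a narcotic. The Background calls it an adjunct. This also stands: the mechanism is possible but not demonstrated.

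Third, a reader might infer that the regimen adds an analgesic that historical patients did not have, so that the measure is biased in favour of tizanidine. The documents do not support that. The Background sentence that mentions lower narcotic use begins by saying the drug is already often given after this operation.

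Fourth, a reader might go further and hold that pain claims should rest on the scores alone, with lower narcotic use at unchanged scores counted as substitution. That is unsound too. Scores depend on the analgesia already given. Where staff treat to pain, a real reduction in underlying pain can appear as similar scores with fewer narcotics. A lower need produced by the preoperative dose would not be as-needed substitution at all.

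**Conclusion.** The point holds in a limited form. As written, the plan treats narcotic use as a measure of pain although participants may also receive as-needed tizanidine, and the listed variables cannot tell substitution from pain relief. The conclusion rests on the protocol's own description of the drug and on an unblinded comparison with past data. It does not rest on any observed rate.

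The size is unknown. The relative falls of 10% to 50% in the illustration assume no tizanidine in the historical cohort and no narcotic for any patient whose need tizanidine met. With equal exposure the distortion disappears, and with greater historical exposure it reverses. The documents therefore support saying that the measure may mislead, but not that it is biased toward tizanidine.

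Severity is minor. This is a supplementary measure of a secondary outcome in a pilot study, and it touches neither the primary outcome nor the sample size.

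**What to change.** 1. In the pain paragraph of Methods, delete the words that make narcotic use a proxy. Report narcotic dose in the recovery area as a separate narcotic-use outcome.
2. Add to the Variables list the narcotic, tizanidine and other analgesic doses given in the recovery area, abstracted for the same period in both cohorts. This also shows how much tizanidine historical patients received and whether as-needed doses fall within the recovery stay.
3. Keep the 0-10 score as the main pain measure and state that it will be interpreted jointly with analgesic use.
4. State in advance that lower narcotic use with unchanged scores does not by itself establish either pain reduction or substitution.

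The cost is a few sentences and a little more chart abstraction, including a return to the historical charts if these doses were not recorded there. The pain claim also loses a favourable supporting measure. Treatment of participants does not change.
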